7.6 ALLOWABLE CONCOMITTANT MEDICATIONS AND TREATMENTS

Concomitant psychotropic medication use for the 60 days prior to baseline and during the study is documented at each office visit. Non-psychotropic medications are reviewed by the medication management provider at each visit and the list is retained in source documents (i.e., the local site pharmacy profile from the participant's medical records).

Participants may be maintained on a stable dose of psychotropic medications listed in table below, which has been prescribed for ≥ 2 months and current dose being stable for ≥3 weeks prior to randomization and held constant during the trial.

ALLOWED PSYCHOTROPIC MEDICATIONS		
Antidepressants: Selective Serotonin Reuptake Inhibitors (SSRI)		
Celexa (citalopram)	Luvox (fluvoxamine)	Prozac (fluoxetine)
Lexapro (escitalopram)	Paxil (paroxetine)	Zoloft (sertraline)
Antidepressants: Serotonin–norepinephrine reuptake inhibitors (SNRI)		
Cymbalta (duloxetine)	Fetzima (levomilnacipran)	Pristiq (desvenlafaxine)
Effexor (venlafaxine)	Ixel, Savella, Dalcipran, Toledomin (milnacipran)	
Antidepressants: Serotonin Modulator and Stimulator (SMS)		
Brintellix, Trintellix (vortioxetine)	Desyrel, Oleptro, Trittico (trazodone)	Viibryd (vilazodone)
Antidepressants: Atypical		
Remeron (mirtazapine)	Serzone (nefazodone)	Wellbutrin (bupropion)
Antidepressants: Tricyclic		
Allegron, Aventyl, Noritren, Nortriilen, and Pamelor (nortriptyline)	Elavil (amitriptyline)	Tofranil (imipramine)
Anafranil (clomipramine)	Norpramin (desipramine)	Vivactil (protriptyline)
Aponal, Quitaxon, Sinequan (doxepin)	Pamelor (nortriptyline)	
Asendin (amoxapine)	Surmontil (trimipramine)	
Antidepressants: Monoamine oxidase inhibitors (MAOI)		

ALLOWED PSYCHOTROPIC MEDICATIONS		
Emsam (selegiline)	Marplan (isocarboxazid)	Nardil (phenelzine)
Parnate (tranylcypromine)		
Alpha-1-adrenergic Antagonist		
Minipress (prazosin)		
Non-benzodiazepine Hypnotics		
Ambien (zolpidem)	Imovane (zopiclone)	Lunesta (eszopiclone)
Sonata (zaleplon)		
Non-benzodiazepine Anxiolytic		
BuSpar, Vanspar (buspirone)		
Other		
Neurontin (gabapentin)	Seroquel (quetiapine)	Lamictal (lamotrigine)
Melatonin	Clonidine	If not listed on prohibited medication list, consult with PI or medical monitor for approval.

Participants may attend PTSD support and educational groups and continue with supportive psychotherapy that was initiated prior to study entry.

7.7 ALLOWABLE RESCUE MEDICATIONS

As a provision to support participants who might be in distress during the trial, a medication for severe insomnia and severe agitation is allowed on a case by case basis. From screening to Week 12 and excluding the week prior to CAPS-5 assessments, **diphenhydramine or hydroxyzine** may be used sparingly, defined as up to 50 mg twice per day not to exceed three days per week), for severe insomnia (described as sleeping less than 4 hours per night) or severe agitation (described as persistent and unmanageable), based on the participant's self-report and the Investigator's clinical judgment. **Benzodiazepines are not allowed.**

7.8 PARTICIPANT ACCESS TO STUDY AGENT AT STUDY EXIT

Naltrexone is currently on VA formularies and the participant may have access to this medication from his/her clinic provider. Although SL-BUP is on VA formulary, it is not currently indicated for AUD or PTSD.

8 ASSESSMENTS OF SAFETY AND ADVERSE EVENTS

8.1 SPECIFICATION OF SAFETY PARAMETERS

At each visit participants are asked by the CRC and/or investigator if they are experiencing any discomfort or symptoms that might indicate potential side effects of the study drug. Any reported complaints are documented by the CRC or investigator and, if serious, are reported to the IRB (per local IRB reporting requirements) and the DSMB (in regularly scheduled DSMB reports).

8.1.1 DEFINITION OF ADVERSE EVENTS (AE)

An Adverse Event (AE) is any untoward medical occurrence temporally related with the use of a drug in humans, whether or not considered drug related per 21 CFR Part 312.32(a). An adverse event (also referred to as an adverse experience) can be unfavorable and unintended sign (e.g., an abnormal laboratory finding), symptom, or disease temporarily associated with the use of a drug and does not imply any judgment about causality. An AE can arise with any use of the drug (e.g., off-label use, use in combination with another drug) and with any route or administration, formulation, or dose, including an overdose. For purposes of this study, a laboratory abnormality (i.e., out of the normal range) that is considered not clinically significant is not considered an AE.

8.1.2 DEFINITION OF SERIOUS ADVERSE EVENTS (SAE)

Serious Adverse Events (SAEs) are defined as any adverse event that in the view of the investigator, results in any of the following outcomes:

- death
- life-threatening
- inpatient hospitalization or prolongation of hospitalization
- persistent or significant disability/incapacity
- congenital anomaly/birth defect

This category includes any other important medical event that an LSI judges to be serious because it may jeopardize the participant or require intervention to prevent one of the above reportable outcomes, or which would suggest a significant hazard, contraindication, side effect, or precaution. Other medically significant events that, based upon appropriate medical judgment, may jeopardize the patient and may require medical or surgical intervention to prevent one of the outcomes listed above (e.g., allergic bronchospasm requiring intensive treatment in an emergency room or home, blood dyscrasias or convulsions that do not result in hospitalization, or the development of drug dependency or drug abuse).

8.1.3 DEFINITION OF UNANTICIPATED PROBLEMS (UP)

The US Department of Health and Human Services Office for Human Research Protections (OHRP) considers unanticipated problems involving risks to participants or others to include any incident, experience, or outcome that meets all the following criteria:

- Unexpected in terms of whether the event exceeds the nature, severity, or frequency given (a) the research procedures that are described in the protocol-related documents, such as the IRB-approved research protocol and informed consent document; and (b) the characteristics of the participant population being studied
- Related or possibly related to participation in the research (“possibly related” means there is a reasonable possibility that the incident, experience, or outcome may have been caused by the procedures involved in the research); and
- Suggests that the research places participants or others at a greater risk of harm (including physical, psychological, economic, or social harm) than was previously known or recognized.

Only a small subset of adverse events occurring in participants are likely to meet these three criteria for an unanticipated problem. Furthermore, there are other types of incidents, experiences, and outcomes that occur during the conduct of human participants’ research that represent unanticipated problems but are not considered adverse events. For example, some unanticipated problems involve social or economic harm instead of the physical or psychological harm associated with adverse events. In other cases, unanticipated problems place participants or others at increased risk of harm, but no harm occurs.

8.2 CLASSIFICATION OF AN ADVERSE EVENT

8.2.1 SEVERITY OF EVENT

Severity of AEs is determined by the LSI or designee using *FDA’s Guidance for Industry Toxicity Grading Scale for Healthy Adult and Adolescent Volunteers Enrolled in Preventive Vaccine Clinical Trials*, as a guide. General parameters for each grade are as listed in table below.

General Parameters for Grading an Adverse Event				
Vital Signs*	Mild (Grade 1)	Moderate (Grade 2)	Severe (Grade 3)	Potentially Life Threatening (Grade 4)
Fever (°F) **	100.4 – 101.1	101.2 – 102.0	102.1 – 104	> 104
Tachycardia - beats per minute	101 – 115	116 – 130	> 130	ER visit or hospitalization for arrhythmia
Bradycardia - beats per minute***	50 – 54	45 – 49	< 45	ER visit or hospitalization for arrhythmia
Hypertension (systolic) - mm Hg	141 – 150	151 – 155	> 155	ER visit or hospitalization for malignant hypertension
Hypertension (diastolic) - mm Hg	91 – 95	96 – 100	> 100	ER visit or hospitalization for malignant hypertension
Hypotension (systolic) – mm Hg	85 – 89	80 – 84	< 80	ER visit or hospitalization for hypotensive shock

Respiratory Rate – breaths per minute	17 – 20	21 – 25	> 25	Intubation
* Participant should be at rest for all vital sign measurements.				
** Oral temperature; no recent hot or cold beverages or smoking.				
*** When resting heart rate is between 60 – 100 beats per minute. Use clinical judgement when characterizing bradycardia among some healthy participant populations, for example, conditioned athletes.				
Systemic (General)	Mild (Grade 1)	Moderate (Grade 2)	Severe (Grade 3)	Potentially Life Threatening (Grade 4)
Nausea or vomiting	No interference with activity or 1 – 2 episodes/24 hours	Some interference with activity or > 2 episodes/24 hours	Prevents daily activity, requires outpatient IV hydration	ER visit or hospitalization for hypotensive shock
Diarrhea	2 – 3 loose stools or < 400 g/24 hours	4 – 5 stools or 400 – 800 g/24 hours	6 or more watery stools or > 800 g/24 hours or requires outpatient IV hydration	ER visit or hospitalization
Headache	No interference with activity	Repeated use of nonnarcotic pain med >24 hrs. or some interference with activity	Significant; any use of narcotic pain reliever or prevents daily activity	ER visit or hospitalization
Fatigue	No interference with activity	Some interference with activity	Significant; prevents daily activity	ER visit or hospitalization
Myalgia	No interference with activity	Some interference with activity	Significant; prevents daily activity	ER visit or hospitalization
Systemic Illness	Mild (Grade 1)	Moderate (Grade 2)	Severe (Grade 3)	Potentially Life Threatening (Grade 4)
Illness or clinical adverse event	No interference with activity	Some interference with activity not requiring medical intervention	Prevents daily activity; requires medical intervention	ER visit or hospitalization
Serum Laboratory*	Mild (Grade 1)	Moderate (Grade 2)	Severe (Grade 3)	Potentially Life Threatening (Grade 4) **
Sodium; Hyponatremia mEq/L	132 – 134	130 – 131	125 – 129	< 125
Sodium; Hypernatremia mEq/L	144 – 145	146 – 147	148 – 150	> 150
Potassium; Hyperkalemia mEq/L	5.1 – 5.2	5.3 – 5.4	5.5 – 5.6	> 5.6
Potassium; Hypokalemia mEq/L	3.5 – 3.6	3.3 – 3.4	3.1 – 3.2	< 3.1
Glucose; Hypoglycemia mg/dL	65 – 69	55 – 64	45 – 54	< 45
Glucose; Hyperglycemia Fasting – mg/random – mg/dL	100 – 110 110 – 125	111 – 125 126 – 200	>125 >200	Insulin requirements or hyperosmolar coma
Blood Urea Nitrogen BUN mg/dL	23 – 26	27 – 31	> 31	Requires dialysis
Creatinine; mg/dL	1.5 – 1.7	1.8 – 2.0	2.1 – 2.5	> 2.5 or requires dialysis
Calcium; hypocalcemia mg/dL	8.0 – 8.4	7.5 – 7.9	7.0 – 7.4	< 7.0
Calcium; hypercalcemia mg/dL	10.5 – 11.0	11.1 – 11.5	11.6 – 12.0	> 12.0
Magnesium; hypomagnesemia mg/dL	1.3 – 1.5	1.1 – 1.2	0.9 – 1.0	< 0.9
Phosphorous (K); hypophosphatemia mg/dL	2.3 – 2.5	2.0 – 2.2	1.6 – 1.9	< 1.6
CPK; mg/dL	1.25 – 1.5 x ULN***	1.6 – 3.0 x ULN	3.1 – 10 x ULN	> 10 x ULN
Albumin; Hypoalbuminemia g/dL	2.8 – 3.1	2.5 – 2.7	< 2.5	--
Total Protein; Hypoproteinemia g/dL	5.5 – 6.0	5.0 – 5.4	< 5.0	--

Alkaline phosphate; increase by factor	1.1 – 2.0 x ULN	2.1 – 3.0 x ULN	3.1 – 10 x ULN	> 10 x ULN
ALT, AST; increase by factor	1.1 – 2.5 x ULN	2.6 – 5.0 x ULN	5.1 – 10 x ULN	> 10 x ULN
Bilirubin; when accompanied by any increase in LFT; increase by factor	1.1 – 1.25 x ULN	1.26 – 1.5 x ULN	1.51 – 1.75 x ULN	> 1.75 x ULN
Bilirubin; when LFT normal; increase by factor	1.1 – 1.5 x ULN	1.6 – 2.0 x ULN	2.0 – 3.0 x ULN	> 3.0 x ULN
Cholesterol	201 – 210	211 – 225	> 226	--
Pancreatic enzymes; amylase, lipase	1.1 – 1.5 x ULN	1.6 – 2.0 x ULN	2.1 – 5.0 x ULN	> 5.0 x ULN
<hr/>				
Hematology*	Mild (Grade 1)	Moderate (Grade 2)	Severe (Grade 3)	Potentially Life Threatening (Grade 4)
Hemoglobin (Female) - gm/dL	11.0 – 12.0	9.5 – 10.9	8.0 – 9.4	< 8.0
Hemoglobin (Female) change from baseline value - gm/dL	Any decrease – 1.5	1.6 – 2.0	2.1 – 5.0	> 5.0
Hemoglobin (Male) - gm/dL	12.5 – 13.5	10.5 – 12.4	8.5 – 10.4	< 8.5
Hemoglobin (Male) change from baseline value – gm/d	Any decrease – 1.5	1.6 – 2.0	2.1 – 5.0	> 5.0
WBC Increase - cell/mm ³	10,800 – 15,000	15,001 – 20,000	20,001 – 25,000	> 25,000
WBC Decrease - cell/mm ³	2,500 – 3,500	1,500 – 2,499	1,000 – 1,499	< 1,000
Neutrophils Decrease - cell/mm ³	1,500 – 2,000	1,000 – 1,499	500 – 999	< 500
Eosinophils - cell/mm ³	650 – 1500	1501 – 5000	> 5000	Hyper-eosinophilic
Platelets Decreased - cell/mm ³	125,000 – 140,000	100,000 – 124,000	25,000 – 99,000	< 25,000
PT – increase by factor (prothrombin time)	1.0 – 1.10 x ULN**	1.11 – 1.20 x ULN	1.21 – 1.25 x ULN	> 1.25 ULN
PTT – increase by factor (partial thromboplastin time)	1.0 – 1.2 x ULN	1.21 – 1.4 x ULN	1.41 – 1.5 x ULN	> 1.5 x ULN
Fibrinogen increase - mg/dL	400 – 500	501 – 600	> 600	--
Fibrinogen decrease - mg/dL	150 – 200	125 – 149	100 – 124	<100; bleeding; disseminated intravascular coagulation
<hr/>				
Urine*	Mild (Grade 1)	Moderate (Grade 2)	Severe (Grade 3)	Potentially Life Threatening (Grade 4)
Protein	Trace	1+	2+	Hospitalization or dialysis
Glucose	Trace	1+	2+	Hospitalization for hyperglycemia
Blood (microscopic); red blood cells per high power field (rbc/hpf)	1 - 10	11 – 50	> 50 and/or gross blood	Hospitalization or packed red blood cells (PRBC) transfusion
* The laboratory values provided in the tables serve as guidelines and are dependent upon institutional normal parameters. ** The clinical signs or symptoms associated with laboratory abnormalities might result in characterization of the laboratory abnormalities as Potentially Life Threatening (Grade 4). For example, a low sodium value that falls within a grade-3 parameter (125-129 mE/L) should be recorded as a grade 4 hyponatremia event if the participant had a new seizure associated with the low sodium value.				
***ULN" is the upper limit of the normal range.				

8.2.2 RELATIONSHIP TO STUDY AGENT

Relationship of AE to study agent is recorded by the LSI or designee and identified as:

Definitely related – the AE can be fully explained by administration of the study drug.

Probably related – the study drug is more likely the cause of the AE than other factors.

Possibly related – there is a reasonable possibility that the study drug is the cause of the AE, including that the study drug and other factor(s) are equally likely as causes of the AE.

Unlikely related – the AE is not a previously known or suspected effect of the test drug, does not follow a sequence of time from drug administration for which the event could be attributed to the administration, and/or cannot be readily explained by the characteristics of the population under study but for which another incontrovertible cause is not immediately identified.

Definitely not related – another factor is clearly (incontrovertibly) the cause of the AE.

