8.2.3 EXPECTED AND ANTICIPATED ADVERSE EVENTS

An unexpected AE experience is any AE in which the frequency, specificity or severity is not consistent with the risk information described in the investigator brochure (e.g., product labeling) or as anticipated from the pharmacological properties of the medication class of the study medication(s). This includes events that are new or greater than previously known in terms of nature, severity, or frequency per the pharmacological properties of the study medications.

Anticipated events, related to both AUD and PTSD, are expected to occur in the study population independent of study medication exposure.

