8.4.2 SERIOUS ADVERSE EVENT REPORTING

Each AE is classified by the LSI or designee as serious or non-serious. SAEs are reported by the LSI to their local IRB, according to that site's local IRB reporting requirements.

The study PI will notify Alkermes (the manufacturer and supplier of XR-NTX and XR-NTX Placebo) of SAEs, that are possibly, probably, or definitely related to study treatment, as quickly as feasible (with a goal of within 24 hours of identification by site personnel).

Initial reports should include as much information as possible but at a minimum should include the event term, onset date, severity, serious criterion, relationship to study drug, date of resolution or continuing (if known), action taken with study drug because of the reported event, and an event outcome (if known).

Initial reporting is followed up with reporting all missing adverse event characteristics and a description of the event. The description provides relevant screening measures, medical history & physical, treatment compliance, reports of other relevant AEs and any other information the LSI deems appropriate. If the participant experiences additional events deemed serious, then these should be reported separately. However, if the participant experiences non-serious AEs during the same period, these are detailed in the SAE description and are reported separately as part of AE collection in the EDC system.

Determination of whether the event may be unexpected and at least possibly temporally related to study drug is made by the LSI in collaboration with the PASA Consortium medical monitor. Any SAE that are deemed at least possibly related and unexpected or unanticipated is submitted by PASA Consortium Leadership, in conjunction with the study team, via study DSMB reviews occurring on a prescheduled frequency.

The medical and research Monitor for this study is:

[name], Medical Monitor and Research Monitor
Vice-Chair of Psychiatry for Research
Houston/Michael E. DeBakey VAMC

The Research Monitor role is a role independent of the research team and is achieved through study oversight as part of the PASA DCC CLT through regular attendance and participation in DSMB meetings, and through ongoing review of SAEs.

The Research Monitor:

- may discuss the research protocol with the investigators, interview human subjects, and consult with others outside of the study about the research, if needed.

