8.5 STUDY HALTING RULES

Study halting rules are determined by the study team and submitted to the PASA Consortium Management. The DSMB will review the halting rules, as part of their protocol review.

A 'study halting rule' typically specifies the outcome differences detected between groups during an interim analysis that can stop a clinical trial or study. Since the sample size for this study is at a minimum to determine a difference between groups, an interim analysis is not planned. Thus, our halting rules reflect guidelines to be considered for temporarily halting or permanently stopping the study.

New Information - There may be new information available to cause the DSMB to halt or stop the study, such as the following:

- The results of other trials indicate that the benefits far outweigh the risks or vice versa,
- A change in the understanding of the underlying biology of the disorders that indicate this pharmacological approach is ineffective or poses a substantial risk to participants,
- A change in the understanding of the pharmacology or interaction of the study drugs, such that the combination poses a substantial risk to participants, or,
- Outside evidence of unacceptable adverse effects from the study drug(s) and/or their interactions.

Safety Reporting - There may be serious adverse reactions reported in which unmasked information would trigger the DSMB to review the study in advance of regularly scheduled meetings and the DSMB may halt enrollment of new participants, such as the following:

- Three (3) Serious Adverse Events in a single organ system or related pathophysiology that are possibly, probably, or definitely related to the drug(s);
- A single occurrence of an unexpected serious and severe, life-threatening adverse event that is uncommon or previously not reported and determined to be strongly associated with drug exposure (e.g., angioedema, aplastic anemia, Stevens-Johnson Syndrome);
- Occurrences of an adverse event determined to be strongly associated with drug exposure that are not commonly associated with drug exposure and otherwise uncommon in the population exposed to the drug.

After review, the DSMB will recommend whether to permanently halt the study, modify the protocol, or continue the protocol. Based on the type of uncommon or previously not reported

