9.5 Safety Analysis Methods

9.5.1 Adverse Events

Any AEs will be listed and summarized by system organ class and preferred event term. Summaries will include the number of individuals experiencing events over the duration of the study. These summaries will be created for all AEs and AEs by severity (mild or moderate vs. severe or greater). Summaries will be provided by treatment group. If models can be run, point and confidence interval estimates of the risk difference will be obtained by modeling the probability of experiencing at least one adverse event. The model is specified with the equation:

$$g(E(Y_{ij})) = \beta_0 + \beta_1 \text{Treatment}_{ij} + s_i + \varepsilon_{ij}$$

Where $g(E(\cdot))$ indicates the identity link function on the expected value of Y , Y_{ij} is the occurrence of an AE outcome (any AE, any SAE, and any related AE) in subject i , β_0 is the intercept, β_1 is the treatment group coefficients, s_i is a random subject effect, and ε_{ij} is the residual error term.

Point and confidence intervals for the difference in experienced AE proportion between treatment groups will be estimated with a generalized linear mixed model (GLMM), assuming a binomial distribution and identity link. GLMMs are a flexible generalization of the linear mixed effect model that allows response outcomes to have an error distribution other than the normal distribution (McCullagh, & Nelder, 1989). Statistical analysis modeling will be carried out utilizing SAS/STAT PROC GLIMMIX (SAS Institute Inc. 2017) with the general structure of the SAS code for this model is listed below:

```
proc glimmix data=anlyaedata;
  class patient treatment;
  model any_ae = treatment / link=identity dist=binomial;
  random int / subject=patient;
run;
```

A similar model will be run for the difference in proportion of withdrawn subjects due to adverse events between treatment groups. If the above specified models cannot be fit due to limitations of the study data, frequencies will be analyzed using chi-square test.

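### Protocol 8.2.2 reverses one ground for *Unlikely related*, so a new, well-timed, unexplained event can be graded below the threshold that four safety rules and one SAP outcome use

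*Protocol*

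**What the plan says.** Protocol 8.2.2 sets a five-grade causality scale. *Unlikely related* has three limbs:

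- A (novelty): "the AE is not a previously known or suspected effect of the test drug"
- B (timing, ending in the connective): "does not follow a sequence of time from drug administration for which the event could be attributed to the administration, and/or"
- C (population): "cannot be readily explained by the characteristics of the population under study but for which another incontrovertible cause is not immediately identified"

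The grade above it, *Possibly related*, applies when "there is a reasonable possibility that the study drug is the cause of the AE". The grade below, *Definitely not related*, needs another factor that is clearly the cause. No rule says which grade prevails when two fit.

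Expectedness is defined separately in 8.2.3, which also says: "Anticipated events, related to both AUD and PTSD, are expected to occur in the study population independent of study medication exposure".

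Several provisions then use a threshold of at least *Possibly related*: mandatory reporting in 8.4.1, notice to the XR-NTX manufacturer in 8.4.2, and the guideline of three SAEs in one organ system in 8.5. So does this sentence of 8.4.2: "Any SAE that are deemed at least possibly related and unexpected or unanticipated is submitted by PASA Consortium Leadership", by way of the scheduled DSMB reviews. SAP 3.2.3 refers to protocol section 8 for relationship definitions, and SAP 9.5.1 models "any AE, any SAE, and any related AE".

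**The concern.** Limb C is reversed. If alcohol use disorder or PTSD does not explain an event and nothing else has been found, the drug becomes a stronger candidate. Limb A is misplaced: whether an effect was previously known is a matter of expectedness, which has its own section. Only limb B is a sound reason to doubt a drug cause.

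The reporting provisions in 8.4 look for events that are both unexpected and at least possibly related. A scale that lets novelty and lack of explanation count towards *Unlikely* works against those provisions on the new reactions they are meant to pick up. The SAP makes relatedness part of its primary safety objective (3.1.1), so the between-arm comparison inherits the same grading.

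**Working it through.** The documents state no figure on this point, so the check is on the wording and its logic.

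**Step 1: polarity of limb C.** Two other places show the intended direction.
- The second half of limb C, about no incontrovertible cause being identified, is introduced by a *but*. That contrast is natural only after a statement that the event *can* be explained. It then separates *Unlikely* (a ready explanation, not proven) from *Definitely not related* (a proven one).
- Section 8.2.3 treats AUD- and PTSD-related events as independent of the drug, the opposite direction from limb C.

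**Step 2: the connective.** Let A = not a known effect, B = implausible timing, C = not explained by the population, with no incontrovertible cause throughout. There are 2 × 2 × 2 = 8 patterns. The test event is new, plausibly timed and unexplained: A = 1, B = 0, C = 1.

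| Reading of 8.2.2 | Patterns that are *Unlikely*, as written | Test event, as written | Test event if only *cannot* becomes *can* |
|---|---|---|---|
| Any limb suffices | 7 of 8 | *Unlikely* | *Unlikely* (novelty alone) |
| (A and B) or C | 5 of 8 | *Unlikely* | not *Unlikely* |
| All three limbs needed | 1 of 8 | not *Unlikely* | not *Unlikely* |

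As written, two of three readings admit the test event. Changing one word is not enough, because under the first reading novelty still qualifies it.

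The all-limbs reading has its own gap. An event with implausible timing that heavy drinking readily explains has C = 0, so it cannot be *Unlikely*. Nor is it *Possibly* unless a drug cause is reasonably possible, so it can fall between grades.

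**Step 3: what an *Unlikely* grade changes.**

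| Provision | Depends on the 8.2.2 grade? |
|---|---|
| 8.4.1 mandatory reporting (conditions read jointly) | Yes |
| 8.4.2 manufacturer notice | Yes |
| 8.4.2 related-and-unexpected SAE submission | Yes |
| 8.5 three-SAE guideline | Yes |
| SAP 9.5.1 related-AE outcome | Yes, though the qualifying grades are not stated |
| 8.5 two guidelines worded as strong association with exposure | No |
| 8.1.3 unanticipated problems | No, it has its own test |
| 8.3 documentation of all AEs | No |
| 8.1 and 8.4.2 SAEs to the local IRB | No |
| SAP Appendix A(d) listing of all AEs for the DSMB | No |
| SAP 9.5.1 any-AE and any-SAE outcomes | No |

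**Step 4: illustration only.** Suppose each drug-caused SAE in one organ system is independently graded *Unlikely* with probability m. With exactly three such SAEs, the chance that all three count towards the 8.5 guideline is (1 − m)³. With five, it is the binomial chance that at least three count.

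| Assumed m | Three SAEs | Five SAEs |
|---|---|---|
| 0.10 | 0.73 | 0.99 |
| 0.25 | 0.42 | 0.90 |
| 0.50 | 0.13 | 0.50 |

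No value of m is given in the documents. Exactly three is the least forgiving case.

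**The case against.** The best defence is that trained assessors would grade sensibly. A new event with plausible timing and no other cause fits *Possibly related* directly, and for SAEs the medical monitor shares the determination of unexpectedness and possible relatedness (8.4.2). A reading that requires all three limbs also keeps the test event out of *Unlikely*. This stands to the extent that misgrading is possible, not certain. It does not rescue the text: two assessors could both follow it and grade the same event differently.

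Three stronger inferences are tempting, and the documents do not support them.

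- *Such events miss every safety trigger.* They do not. The single-event guideline in 8.5, which names angioedema, aplastic anemia and Stevens-Johnson Syndrome as examples, concerns an "unexpected serious and severe, life-threatening adverse event that is uncommon or previously not reported and determined to be strongly associated with drug exposure". That phrase is not a grade on the 8.2.2 scale, so an *Unlikely* grade does not formally block it. The third event guideline in 8.5 is worded similarly.
- *The DSMB would not see them.* Serious complaints go to the DSMB under 8.1 without a relatedness condition, and its report lists all AEs. The 8.5 rules are themselves guidelines, and under 8.6 the DSMB sets the final stopping criteria.
- *Requiring an event to be both unexpected and possibly related is self-contradictory.* It is not. Under 8.2.3 a known effect can be unexpected through its frequency or severity, and such an event does not meet the novelty limb.

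**Conclusion.** The definition is wrong as written, and the severity is moderate. The population limb is reversed, the novelty limb belongs to expectedness, and the and/or allows either to suffice. Together they permit a new, plausibly timed, unexplained event to be graded *Unlikely* under two of three readings. The consequence is limited to four rules and one modelled safety outcome, and arises only when an assessor chooses *Unlikely* over *Possibly*.

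How often that would happen cannot be derived from the documents. A reader might infer that the three-SAE guideline could never be met if the definition were applied literally. That does not follow, because a literal reading also admits *Possibly related* and the all-limbs reading excludes the event. The probabilities in the illustration rest wholly on assumed misgrading rates and independence between events, and they carry no weight in this conclusion.

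**What to change.** In protocol 8.2.2:

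1. Change *cannot* to *can* in the population limb.
2. Remove novelty as a ground for *Unlikely related*, since 8.2.3 covers expectedness.
3. Replace the and/or so that either implausible timing or a ready alternative explanation supports *Unlikely*.
4. State that *Possibly related* prevails whenever a drug cause is reasonably possible.

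Suggested wording:

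> *Unlikely related: the timing in relation to dosing makes a causal link improbable, or the event can readily be accounted for by features of the study population, a concurrent illness or another treatment, without that cause being incontrovertible. If a drug cause nevertheless remains a reasonable possibility, grade the event Possibly related.*

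The two grounds should be alternatives. Requiring both would leave two kinds of event outside *Unlikely*: a well-timed event that drinking explains, and an unexplained event with impossible timing. Under the suggested wording the test event (B = 0, no alternative explanation) meets neither ground.

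In SAP 9.5.1, define a related AE as one graded possibly, probably or definitely related.

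The cost is one reworded definition and one SAP clause. Somewhat more events will be graded *Possibly* and reviewed. If events have already been graded under the present text, the *Unlikely* ones should be reassessed while still masked, so that the related-AE outcome does not mix two definitions.
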